## 5.5 Rule of exclusion criteria of analysis sets

The protocol deviation criteria are listed in the sheet "Protocol Deviations" in the data review plan. The protocol deviation criteria leading to exclusion from the analysis sets are provided in below table, which may be updated prospectively and will be finalized before database lock.

**Table 5-3 Protocol deviation criteria leading to exclusion from the analysis sets**

Protocol Deviation		Excluding from Analysis Set				
ID	Description	SCR	RAS	FAS	SAF	OLS
INCL01A	Written informed consent not obtained.	X	X	X	X	X
TRT03	Subject was not randomized but took study drug		X	X	X	X
OTH07	Participant was randomized in error but did not receive IMP			X	X	X
OTH01A	Site closed down for GCP reasons during Core part.				X	
OTH01B	Site closed down for GCP reasons during Extension.					X

Below table presents patient classification criteria including protocol deviation criteria and non-protocol-deviation criteria leading to exclusion from analysis sets.

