9.1 Analysis sets

The following analysis sets will be used for statistical analyses:

The screened set (SCR) consists of all participants who signed the informed consent. The SCR includes only unique screened participants, i.e., in the case of re-screened participants only the chronologically last screening data is counted.

The Randomized Analysis Set (RAS) consists of all participants who received a randomization number, regardless of receiving trial medication.

The Full Analysis Set (FAS) consists of all randomized participants with the exception of those participants who have not been qualified for randomization and have not received study drug, but have been inadvertently randomized into the study. Following the intent-to-treat (ITT) principle, participants will be analyzed according to the treatment they have been assigned to at randomization.

The Safety Analysis Set (SAF) includes all participants who received at least one dose of study drug. Participants will be analyzed according to the study treatment actually received.

Note: The last part of the definition of the FAS is what is often referred to as mis-randomized participants i.e. participants for whom IRT calls were made by the site either prematurely or inappropriately prior to confirmation of the participant's final randomization eligibility and double-blind medication was not administered to the participant. These participants would subsequently not continue to take part in the study or be followed-up. Mis-randomized participants will not be included in the FAS, but they will be included in the RAS. Further

exclusions from the FAS may only be justified in exceptional circumstances (e.g., serious Good Clinical Practice (GCP) violations).

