## Assessments and events allocation

In general, assessments and events will be allocated into the screening period, the core part and the extension part using the following rules.

- For non-randomized participants, all assessments / events will be considered as screening period assessments / events.
- For randomized participants, assessments / events with assessment date / event date prior to the randomization visit date will be considered as screening period assessments / events.
- For randomized participants with missing switching date, assessments / events with assessment date / event date on or after the randomization visit date will be considered as core part assessments / events.
- For randomized participants with non-missing switching date, assessments / events with assessment date / event date on or after the randomization visit date and on or prior to the switching date will be considered as core part assessments / events.
- For randomized participants with non-missing switching date, assessments / events with assessment date / event date after the switching date will be considered as extension part assessments / events.

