## 2.2 Analysis sets

The following analysis sets will be used for statistical analyses:

The **Screened Set (SCR)** consists of all participants who signed the informed consent. The SCR includes only unique screened participants, i.e., in the case of re-screened participants only the chronologically last screening data is counted.

The **Randomized Analysis Set (RAS)** consists of all participants who received a randomization number, regardless of receiving trial medication.

The **Full Analysis Set (FAS)** consists of all randomized participants with the exception of those participants who have not been qualified for randomization and have not received study drug but have been inadvertently randomized into the study. Following the intent-to-treat (ITT) principle, participants will be analyzed according to the treatment they have been assigned to at randomization. Efficacy variables will be analyzed based on the FAS.

The **Safety Analysis Set (SAF)** includes all participants who received at least one dose of study drug. Participants will be analyzed according to the study treatment actually received. The SAF will be used for the analyses of safety variables.

[figure not shown]
The **Open-label Set (OLS)** includes all participants who entered the extension part and received at least one dose of study drug during extension part (at Day 180 or Day 270). OLS will be used to analyze the non-efficacy data in extension part, unless otherwise specified.

Participants without valid written informed consent will be excluded from all analysis sets. Further exclusions from the FAS are only justified in exceptional circumstances (e.g., site closed down for GCP reasons). The determination of which participants were excluded from the FAS is made in a blinded manner before the database lock for the Core Part.

Rules leading to exclusion from the analysis sets are given in [Appendix 5.5](#).

Note: The last part of the definition of the FAS is what is often referred to as mis-randomized participants i.e. participants for whom IRT calls were made by the site either prematurely or inappropriately prior to confirmation of the participant's final randomization eligibility and study medication was not administered to the participant. These participants would subsequently not continue to take part in the study or be followed-up. Mis-randomized participants will not be included in the FAS, but they will be included in the RAS.

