## **4 Change to protocol specified analyses**

NA

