**Table 5-4 Patient classification**

Analysis Set	Protocol Deviation ID leading to exclusion of patients	Non-protocol deviation criteria leading to exclusion from analysis sets
SCR	INCL01A	Not applicable
RAS	INCL01A, TRT03	

• Patient without a randomization number

FAS	INCL01A, TRT03, OTH07, OTH01A, OTH01B	

• Patient without a randomization number

SAF	INCL01A, TRT03, OTH07	

• Patient without a randomization number

OLS	INCL01A, TRT03, OTH07	

• Patient without a randomization number

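### SAP Tables 5-3 and 5-4 remove dosed but unrandomised participants from a Safety Analysis Set that the protocol defines by dosing alone, and SAP Section 4 declares no change

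*SAP*

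**What the plan says.** **Definitions.** Protocol 9.1 states: "The Safety Analysis Set (SAF) includes all participants who received at least one dose of study drug". SAP 2.2 says the same of the SAF, which "includes all participants who received at least one dose of study drug". Both analyse participants by the treatment they actually received. SAP 2.2 defines the OLS in the same spirit: it "includes all participants who entered the extension part and received at least one dose of study drug during extension part". The only exclusion from every set that the text of SAP 2.2 names is lack of valid written consent.

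**Exclusion rules.** SAP 2.2 then says "Rules leading to exclusion from the analysis sets are given in" Appendix 5.5. There, Table 5-3 marks TRT03, "Subject was not randomized but took study drug", as excluded from the RAS, FAS, SAF and OLS, but not from the screened set. In Table 5-4 the SAF and OLS rows both list TRT03 and also give "Patient without a randomization number" as a criterion that is not a protocol deviation.

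**Declared changes.** The entry under SAP Section 4, "Change to protocol specified analyses", is NA.

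**Allocation to study parts.** SAP 2.1.1 says: "For non-randomized participants, all assessments / events will be considered as screening period assessments / events". Each core-part and extension-part rule in that section is written for randomised participants only.

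**The concern.** A TRT03 participant has been dosed, by the wording of the deviation itself. That person meets the SAF definition in both documents and is then removed by the appendix. Excluding TRT03 from the RAS and FAS is right, because both sets rest on randomisation. The SAF does not.

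SAP 2.7 makes the SAF the default set for all safety analyses, and the adverse event tables for ClinicalTrials.gov are also built on the safety set. The stake is that an exposed participant's adverse events drop out of those tables under a rule that the protocol does not contain and the SAP does not declare.

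**Working it through.** The plan gives no figure to reproduce, so the main check is a comparison of the texts.

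**1. Does a TRT03 participant meet the SAF definition?** The definition needs one dose, and TRT03 means that study drug was taken. With valid consent, the answer is yes under Protocol 9.1 and under the text of SAP 2.2.

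**2. Do the tables remove that participant?** Yes, in three places: the TRT03 mark under SAF in Table 5-3, TRT03 in the SAF row of Table 5-4, and the randomisation-number criterion in that same row. The second and third are plain text in a row, so a shifted column in Table 5-3 would not explain the finding.

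**3. Does the SAF row test what the definition tests?** No. Its only criterion that is not a protocol deviation is the one used for the RAS, possession of a randomisation number. It has no dosing criterion of its own.

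**4. Is the narrowing declared?** No. Section 4 reads NA.

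**5. Would correcting the tables be enough?** No. Under the SAP 2.1.1 rule quoted above, all data from this participant would go to screening. SAP 2.7.1, in contrast, treats an event as treatment-emergent if it starts on or after first dose, and splits such events by switching date. The laboratory shift tables in SAP 2.7.3 are by study part but bring no part rule of their own. A dosed, unrandomised participant could therefore enter the SAF with no usable study part.

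**6. Size.** Inputs: 100 participants per arm (Protocol 6.1.2). The number omitted is an assumption, since the documents give no count. Let x be the number of participants with the event in the arm when everyone dosed is included.

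- One omitted, who had the event: x/101 − (x−1)/100 = (101−x)/10100. This is largest at x = 1: 100/10100 = 0.99 percentage points.
- One omitted, who did not have it: x/101 − x/100 = −x/10100. This is largest in size at x = 100, again 0.99 points.
- Two omitted, both with the event: x/102 − (x−2)/100 = (204−2x)/10200. This is largest at x = 2: 200/10200 = 1.96 points.

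The largest relative effect arises when the omitted participant has the arm's only event:

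| Rule | Events / n | Incidence | Exact 95% CI |
|---|---|---|---|
| Dosing definition | 1/101 | 0.99% | 0.03% to 5.39% |
| Tables 5-3 and 5-4 | 0/100 | 0% | 0% to 3.62% |

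The intervals are Clopper-Pearson; for 0/100 the upper limit is 1 − 0.025^(1/100) = 3.62%. They overlap widely. The table is an illustration, not a forecast. With no TRT03 case, no number changes.

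**The case against.** **The SAP can be read as a definition less listed exclusions.** SAP 2.2 sends the reader to Appendix 5.5, and the exclusion fits the rule that places unrandomised participants' data in screening. It may be deliberate. This may reconcile the SAP with itself. It does not reconcile it with Protocol 9.1, which has no such carve-out, or with NA in Section 4.

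**Cases should hardly occur.** Site staff obtain kit numbers from the IRT (Protocol 6.2), and the IRT gives the randomisation number and the first kit number at the same step (Protocol 6.3.1). A TRT03 case needs that process to be bypassed. This stands, and it is why the effect is minor. The case is still foreseen: the sponsor wrote a deviation code for it, and Protocol 8.6.3 sets SAE reporting for participants who are randomised or treated.

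**The exclusion would not be hidden.** SAP 2.3.1 requires exclusions from analysis sets to be summarised and listed with reasons, in both the core and final analyses. A TRT03 participant stays in the screened set. SAP 2.7.1 promises a listing of all AEs and SAEs, and SAEs reach sponsor safety in any case. This also stands, with one reservation: because SAP 2.7 defaults to the SAF, the AE listing may itself be limited to that set.

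**Stronger readings.** A reader might infer that the safety results are biased or that harms are being concealed. The documents do not support that: they show no case, the largest effect of one case is under one percentage point, and the exclusion must be reported with its reason. A reader might also infer a second error, because the site-closure entries appear to differ between Tables 5-3 and 5-4. That may be a column shift in the PDF conversion, and SAP 2.2 already has FAS exclusions settled blind before the Core Part lock. It forms no part of this point.

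**Conclusion.** The point holds as an inconsistency with the protocol that should be corrected. Either the SAF entries in Tables 5-3 and 5-4 or the NA in Section 4 is wrong as written. The OLS entries conflict with the dosing-based OLS definition in SAP 2.2 in the same way.

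The practical effect is minor: at most 0.99 percentage points on an arm's incidence for one omitted participant, and nothing if none exists. This assumes 100 per arm and a consented participant. The primary and other efficacy analyses are unaffected, because the FAS requires randomisation in any case.

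**What to change.** 1. In Table 5-4, delete TRT03 and the randomisation-number criterion from the SAF row. In Table 5-3, delete the TRT03 mark under SAF. Make the OLS entries follow the dosing-based definition in SAP 2.2. Leave the RAS and FAS entries for TRT03 as they are.
2. Analyse any such participant by treatment actually received, and footnote the affected tables.
3. Amend the allocation rules in SAP 2.1.1. Data from a dosed but unrandomised participant on or after first dose should go to the core or extension part by the switching-date rule used for randomised participants, and to the core part if the switching date is missing. This agrees with the first-dose rule in SAP 2.7.1.

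Alternatively, if the sponsor wishes to keep the exclusion, declare it in Section 4 as a change from Protocol 9.1 and list these participants' adverse events separately.

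The cost is an edit to two tables and one amended rule, with no new data. If a case exists, the affected core-part safety tables would have to be rerun. The SAF may then contain a participant who was not randomised, which the footnote makes visible.

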**Table 5-4 Patient classification**

Analysis Set	Protocol Deviation ID leading to exclusion of patients	Non-protocol deviation criteria leading to exclusion from analysis sets
SCR	INCL01A	Not applicable
RAS	INCL01A, TRT03	

• Patient without a randomization number

FAS	INCL01A, TRT03, OTH07, OTH01A, OTH01B	

• Patient without a randomization number

SAF	INCL01A, TRT03, OTH07	

• Patient without a randomization number

OLS	INCL01A, TRT03, OTH07	

• Patient without a randomization number

